2.1.4 Definition of terms included in study endpoints

2.1.4.1 Efficacy endpoints

Please refer to the document “Important derivations in AMG” (in CREDI: AMG334A/Administrative files/CIS (Clinical Information Sciences)/Biostatistics) for more detail on the derivations. Derivations will be based on eDairy data and done by analysis team.

eDiary Day

A day in which a subject uses the eDiary.

Information Day

A day which is either a headache day or an eDiary day.

Migraine Day

A migraine day is defined as any calendar day in which the subject experiences a qualified migraine headache (onset, continuation, or recurrence of the migraine headache). Please see exceptions in [Appendix 5.10](#). A qualified migraine headache is defined as a migraine with or without aura, lasting for ≥ 4 continuous hours, and meeting at least one of the following criteria:

1. ≥ 2 of the following pain features:

- Unilateral
- Throbbing
- Moderate to severe
- Exacerbated with exercise/physical activity

2. ≥ 1 of the following associated symptoms:

- Nausea and/or vomiting
- Photophobia and phonophobia

If the subject took ANY acute medication (simple analgesics [NSAIDs, acetaminophen], combination analgesics, triptans or ergot-derivative) during aura, or to treat a moderate or severe headache on a calendar day, then it will be counted as a migraine day regardless of the duration and pain features/associated symptoms. Opioid-containing analgesic and butalbital-containing analgesic are excluded in allowed acute medication categories.

Monthly Migraine Days

Number of migraine days between each monthly IP dose that are normalized in a 28-day interval. Monthly migraine days at baseline are the number of migraine days in the baseline period that are normalized in a 28-day interval. Days without eDiary data in each normalized monthly interval will be prorated. All details of calculation are in [Section 5.1.5](#) (The same proration method will be applied for other efficacy endpoints thereafter).

Modified Migraine Disability Assessment (mMIDAS)

The modified Migraine Disability Assessment Questionnaire (mMIDAS) is a 5-item self-administered questionnaire that sums the number of productive days lost over the past month in two settings: the workplace and the home. The mMIDAS also assesses disability in family, social, and leisure activities. The mMIDAS score is the sum of missed days due to a headache from paid work, housework, and non-work (family, social, leisure) activities; and days at paid work or house work where productivity was reduced by at least half. **The total score is**

multiplied by 3 and categorized into 4 severity grades: Grade I = 0 - 5 (defined as minimal or infrequent disability), Grade II = 6 - 10 (mild or infrequent disability), Grade III = 11 - 20 (moderate disability), and Grade IV = 21 and over (severe disability). The recall period is the past one month.

Subjects will complete the mMIDAS monthly using the eDiary. Please refer to [Appendix 5.9](#) for scoring algorithm.

Achievement of at least a certain percentage reduction from baseline in monthly migraine days

Calculated based on the following: (monthly migraine days at each timepoint post-baseline - baseline monthly migraine days*100/baseline monthly migraine day.

At least a 50% reduction at month [REDACTED] will be evaluated.

Monthly Acute Headache Medication Treatment Days

Number of days on which acute headache medications are used as recorded in eDiary between each monthly IP dose. Monthly acute headache medication treatment days at baseline are the number of acute headache medication treatment days in the baseline period. Days without eDiary data are handled by proration according to [Section 5.1.5](#).

Unknown medications (entered as 'Other' in the eDiary and not identified) will not be counted as acute headache treatment. Sensitivity analysis might be performed as appropriate.

Headache Day

[figure not shown]
A headache day is any calendar day in which the subject experiences a qualified migraine or non-migraine headache (initial onset, continuation or recurrence of the headache). Please see exceptions in [Appendix 5.10](#). A qualified headache is defined as:

- a qualified migraine headache (including an aura-only event that is treated with acute migraine-specific medication), or

- a qualified non-migraine headache, which is a headache that lasts ≥ 4 continuous hours and is not a qualified migraine headache, or
- a headache of any duration for which acute headache treatment is administered.

The headache day will be flagged in eDiary data.

2.1.4.2 Safety endpoints

Subject Incidence

The subject incidence for a given event in a given period is defined as the number of subjects with at least one reported occurrence of the event divided by the number of subjects who entered that period. For subjects with multiple occurrences of the same event, the event will only be counted once per subject.

Exposure-Adjusted Subject Incidence Rate

The exposure-adjusted subject incidence rate for a given event in a given period is defined as the number of subjects with at least one reported occurrence of the event in a given time period divided by total subject years at risk in that period. The time at risk for each subject will differ for each adverse event. For subjects with events, only the time until the first event contributes to the total subject years at risk. For subjects who do not experience the event, the time at risk will be up to the last available visit. This rate will be presented per 100 subject years. For subjects with multiple occurrences of the same event, the event will be only counted once per subject.

Treatment-Emergent Adverse Event (TEAE)

Adverse Events (AEs) recorded on the Adverse Events eCRF page that occurs on or after first dose of investigational product and up to and including end of study.

Serious Adverse Event (SAE)

SAEs determined by the flag indicating if the adverse event is serious on the Adverse Events eCRF page will include those that occur after signing of the informed consent and up to and including end of study.

Treatment-Emergent Serious Adverse Event

A treatment-emergent serious adverse event is an SAE considered to be treatment-emergent.

Treatment-Related Adverse Event

A treatment-related AE is defined as a treatment-emergent adverse event that is considered by investigators to have reasonable possibility that it may have been caused by IP as determined by the flag indicating that there is a reasonable possibility that the AE is related to investigational product on the Adverse Events eCRF page.

Treatment-Related Serious Adverse Event

A treatment-related serious adverse event is an SAE considered to be treatment-related.

Adverse Event leading to discontinuation of study treatment

An AE leading to discontinuation of study treatment will be identified by the item “Action Taken With Study Treatment” on AE page of CRF when it’s reported as “Drug withdrawn”.

Serious Adverse Event leading to discontinuation of study treatment

An SAE that is considered to lead to discontinuation of study treatment.

Columbia-Suicide Severity Rating Scale (C-SSRS)

The Columbia-Suicide Severity Rating Scale (C-SSRS) is a questionnaire that prospectively assesses Suicidal Ideation and Suicidal Behavior. The C-SSRS must be administered at each visit, including unscheduled visits.

Two versions depending on the type of visits will be used in this study: Screening and Since Last Visit. The C-SSRS consists of a maximum of 20 items to evaluate suicidal behavior and suicidal ideation.

Prior, concomitant medication

Prior medication will be defined as any non-study medication taken prior to the first dose of the randomized study medication, irrespective of whether the medication continued into the treatment period.

Any non-study medication administered at least once between the day of first dose of randomized study medication and end of study will be a concomitant medication.

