All subjects ongoing in the treatment period at the time of a positive IA read-out will be scheduled for an End of Treatment visit and then enter directly into the open-label treatment period or into the safety Follow-Up Period (in case the subject does not want to continue in the open-label treatment period) without performing those FUP visits.

Subjects who discontinue the study treatment in the double-blind treatment period and are NOT willing to return for the subsequent FUP visits should perform the assessments according to the End of Treatment visit as soon as possible and the following data should be collected after study treatment discontinuation and until the Safety Follow-Up visit (which should occur 12 weeks after the last dose):

- new / concomitant treatments
- adverse events/Serious Adverse Events

If the subject who discontinued study treatment in the double-blind treatment period cannot or is unwilling to attend the End of Treatment visit or the Safety Follow-Up visit, the site staff should maintain telephone contact with the subject, or with a person pre-designated by the subject.

Subjects who discontinue the treatment during the open-label treatment period and performed the End Of Treatment visit will not be allowed to re-enter the study.

The investigator must also contact the IRT to register the subject's discontinuation from study treatment.

If study drug discontinuation occurs because the treatment code has been broken, please refer to [Section 6.6.2](#). Subjects who are prematurely withdrawn from the study will not be replaced by an equal number of newly enrolled subjects.

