2.1 Data analysis general information

Data from the study will be analyzed based on the study phase as defined in Table 2-1. The full scope of data analysis defined in this document is pertinent to both DB period (including safety follow-up), and OLE period. The sub-scope of data analysis for the unblinded interim readout is defined in section 2.12.

Table 2-1 Study Phases for data analysis

Study Phase	Start Time Point	End Time Point
DB Period (including Safety follow-up)	Study Day 1 (after the 1st DB IP Dose)	For subject who won't join in OLE: end of study date; For subject who join in OLE: the End of Treatment visit in DB period (the last visit scheduled in DB Period)
OLE Period (applicable for subjects continuing OLE treatment)	The End of Treatment Visit in DB Period + 1	For subject who join in OLE: end of study date

*In general, if the End of Treatment visit date of DB period and the 1st OLE IP injection are on the same day, then the AE or CM which occurs on that day will be considered to belong to DB

period. [REDACTED]

In the case of a positive unblinded IA read-out (success), an interim CSR based on the 70% subjects (DB period completers or early withdrawers up to the unblinded IA cutoff) who are included in the unblinded IA analysis will be generated. The primary analysis will be performed for DB period. Ongoing DB period subjects at the time of unblinded IA cutoff will not be included in this interim CSR. Their data will be reported in an addendum for the interim CSR, when all subjects completed their last visit in DB period. In this interim CSR addendum, those ongoing subjects together with the 70% subjects who have been included in the interim CSR, will be analyzed again and data will be mainly presented by summary statistics. The interim CSR and its addendum will be prepared for regulatory submission.

In case the trial needs to continue enrollment to full sample size as all enrolled subjects have completed DB period, the primary database lock will then be performed. One interim CSR based on all data from DB period and safety follow up collected up to the cutoff timepoint for the primary lock will be prepared for regulatory submission.

At the end of OLE period, a final CSR for data from OLE will be prepared supplementally.

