2.1.1.1 Study dates

eDiary Device Assignment Date

The date on which an eDiary device is assigned to a subject for the first time after completion of initial screening at week -4 visit.

Randomization (Enrollment) Date

Randomization (Enrollment) Date is the date on which a subject is assigned to one of the treatments through IRT in DB period.

First DB IP Dose Date

The first DB IP dose date is the date on which a subject is administered the first dose of IP following randomization, which may be the same day (most of the time) or after the randomization date. For subjects who are randomized but never dosed with double-blind IP after randomization, First DB IP Dose Date is considered missing.

Last DB IP Dose Date

The last DB IP dose date for each subject is defined as the latest date IP is administered during DB period.

First OLE IP Dose Date

The first OLE IP dose date is the date on which a subject is administered the first OLE dose of IP on or after Week 12. The first OLE IP dose date will only be applicable for subjects who enter OLE period.

Last OLE IP Dose Date

The last OLE IP dose date for each subject is defined as the latest date IP is administered during OLE period, which is applicable for subjects who enter OLE period.

Subject-level End of DB Treatment (EOT DB) Date

The end of DB treatment date for each subject is defined as the end of the treatment in DB period. The date will be recorded on the Treatment disposition eCRF page.

Subject-level End of OLE Treatment (EOT OLE) Date

The end of OLE treatment date for each subject is defined as the end of the treatment in OLE period. The date will be recorded on the Open-label Treatment disposition eCRF page.

Subject-level End of Study (EOS) Date

The end of study (EOS) date for each subject is defined as the last date on which the subject participated in the study. The date will be recorded on the Study disposition eCRF page.

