2.3 Subject disposition, demographics and other baseline characteristics

2.3.1 Subject disposition

Randomized

Subjects are considered randomized if they have been assigned a randomization number.

Exposed to Investigational Product

Subjects are defined as being exposed to IP if they receive at least one dose of IP.

Completing the DB Treatment

Subjects are defined as completing the treatment period if they receive the week 8 IP dose. It will be derived from Treatment Disposition Form with “Completed” as subject status.

Completing the DB period

Subjects are defined as completing the DB period if they complete all visits up to EOT assessments at Week 12.

Entering into the OLE Period

Subjects are considered entering into OLE period if they complete the DB period and sign on ICF for OLE period.

Completing the Study

Subjects are defined as completing DB period if they complete the safety follow-up visit (week 20), or continue with OLE treatment until the end of study. It will be derived from Study Disposition Form with “Completed” as subject status.

Subject disposition for DB period will be displayed by randomized treatment and overall on FAS, in terms of:

- the number and percentage (based on the number of subjects within each randomized treatment arm) of subjects who complete the DB treatment, or discontinue the DB treatment prematurely along with the primary reason
- the number and percentage of subjects who has completed DB period and enter into OLE period or safety follow-up visit
- the number and proportion of subjects, who complete the DB period, or discontinue the DB period prematurely along with the primary reason for study

The subject disposition for OLE period will be summarized on OAS, in terms of:

- the number and percentage of subjects who complete the OLE treatment, or discontinue the OLE treatment prematurely along with the primary reason
- the number and percentage of subjects who complete the OLE period, or discontinue the OLE period prematurely along with the primary reason

In addition, the total number of subjects screened and the number of subjects screened, but not randomized (discontinued prior to screening phase completion or prior to baseline period completion) will be summarized, including the reason for non-inclusion into the study.

The number of subjects within each of the analysis sets used in the study will be given.

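### Exposure-adjusted AE rates count events to end of study but stop event-free time at the last visit, which slightly overstates rates where AE follow-up continues after that visit

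*SAP*

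**What the plan says.** SAP 2.1.4.2 defines the exposure-adjusted subject incidence rate as subjects with at least one event divided by total subject-years at risk in the period. Three rules set the time involved.

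- Subjects with an event: "For subjects with events, only the time until the first event contributes to the total subject years at risk".
- Subjects without one: "For subjects who do not experience the event, the time at risk will be up to the last available visit".
- Numerator: a TEAE is an event "that occurs on or after first dose of investigational product and up to and including end of study".

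SAP 2.1.1.1 does not tie end of study to a visit: "The end of study (EOS) date for each subject is defined as the last date on which the subject participated in the study". Table 2-1 in SAP 2.1 closes the double-blind phase, which includes safety follow-up, in one of two ways: "For subject who won't join in OLE: end of study date", or "For subject who join in OLE: the End of Treatment visit in DB period".

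Protocol Table 8-1 (footnote 14) collects adverse events to 12 weeks after the last dose. For a discontinuer who cannot attend or is "unwilling to attend the End of Treatment visit or the Safety Follow-Up visit, the site staff should maintain telephone contact with the subject" (Protocol 9.1.1). SAP Table 2-4 plans the exposure-adjusted rate for every AE category, from all TEAEs to deaths.

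**The concern.** The numerator and the denominator are cut at different points. If a subject is followed for AEs after the last visit, an event in that stretch enters the numerator, and that subject's time to the event is credited. A subject followed over the same stretch without an event gets no credit for it. Person-time is lost only from the event-free, so the rate can only go up.

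The protocol creates such stretches in two ways. Discontinuers who decline visits may be followed by telephone alone. Completers not entering open-label treatment have no scheduled visit between Week 12 and Week 20. Some may be in that interval at the cut-off, and Protocol 12 includes the safety follow-up data available by then.

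This rate is the SAP's own correction for unequal follow-up, so its denominator should measure follow-up correctly.

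**Working it through.** The documents state no exposure-adjusted rate, no subject-years and no discontinuation rate by arm, so there is no plan figure to reproduce. The rules come first, then the size.

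**Who is affected**

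| Subject | Events counted to | Event-free time to | Gap |
|---|---|---|---|
| Enters open-label treatment | DB End of Treatment visit | same visit | none |
| Completer, attends Week 20 | end of study, at that visit | same visit | none |
| Discontinuer, attends safety follow-up | end of study, at that visit | same visit | none |
| Discontinuer, telephone only at the end | end of study | last visit attended | yes |
| Completer between Weeks 12 and 20 at cut-off | cut-off | Week 12 visit | yes, under 8 weeks |

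Time at risk runs without a break up to the last visit, so intervals between attended visits are counted in full.

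**Inputs from the documents.** Dropout is 10% overall (SAP 3; Protocol 12.8.1). The window is 12 weeks for open-label entrants and 20 weeks for other completers. For discontinuers it is last dose plus 12 weeks.

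**Assumptions, not in the documents.** Last doses of discontinuers are spread equally over Day 1, Week 4 and Week 8, giving windows of 12, 16 and 20 weeks (mean 16). The telephone-only share, the gap after the last visit and open-label uptake are varied. The event rate is constant at 13 per 100 subject-years.

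**Formula.** With *d* the proportion discontinuing, *p* the telephone-only share of them, *g* the gap in weeks and *T* the mean true window, the rate is multiplied by approximately *T* / (*T* − *d·p·g*).

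- No open-label uptake: *T* = 0.90×20 + 0.10×16 = 19.6 weeks.
- 90% uptake among completers: their mean is 0.9×12 + 0.1×20 = 12.8, so *T* = 0.90×12.8 + 0.10×16 = 13.12 weeks.

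| Case (*d* = 10%) | Weeks lost per subject | Approximate factor | Constant-hazard rate (true 13.0) |
|---|---|---|---|
| Mild: *p* 25%, *g* 4, no uptake | 0.1 | 19.6/19.5 = 1.005 | 13.07 (+0.5%) |
| Middle: *p* 50%, *g* 8, no uptake | 0.4 | 19.6/19.2 = 1.021 | 13.27 (+2.1%) |
| Middle: *p* 50%, *g* 8, 90% uptake | 0.4 | 13.12/12.72 = 1.031 | 13.40 (+3.1%) |
| Extreme: *p* 100%, *g* 12, 90% uptake | 1.2 | 13.12/11.92 = 1.101 | 14.28 (+9.8%) |

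The last column is slightly lower in the extreme case because subjects with events keep their full time. With one window for numerator and denominator, the rate returns to 13.0 in every case.

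**Between arms.** With equal discontinuation and equal telephone-only follow-up, the distortion of the rate ratio is 0%. Take 5% against 10% discontinuing in the middle case:

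- No uptake: the 5% arm has *T* = 0.95×20 + 0.05×16 = 19.8 and loses 0.2, a factor of 19.8/19.6 = 1.010. The ratio is 1.021/1.010, about +1.1%.
- 90% uptake: *T* = 0.95×12.8 + 0.05×16 = 12.96, a factor of 12.96/12.76 = 1.016. The ratio is 1.031/1.016, about +1.5%.

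The extreme case gives about +4.9%. Completers awaiting Week 20 at the cut-off are not in these figures, because the documents do not say how many there will be.

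**The case against.** The case for leaving the text alone has real substance.

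**Few subjects have a gap.** Everyone completing on drug is invited into open-label treatment, and everyone else has a planned safety follow-up visit. Telephone contact is the fallback for those who will not attend. Subjects who withdraw consent contribute no later follow-up. Protocol 4.5 cites about 95% retention on active treatment at 3 months. This stands, and it is why the likely effect is a few per cent at most.

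**A telephone contact may already be a visit.** Protocol 8 lets calls and virtual contacts replace on-site visits during the pandemic. The SAP does not say whether such a contact counts as an available visit, and outside the pandemic provision the question is open. This could shrink the gap. It also means two programmers could derive different denominators, which is itself a reason to settle the wording.

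**Censoring at the last visit is defensible,** because AEs are actively sought at visits (Protocol 10.1.1). That is a fair reason for the denominator, but it would require cutting the numerator at the same point, and the SAP does not do so.

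**Nothing is decided on these rates.** SAP 2.7 rules out testing between arms, and crude incidence, which this rule does not touch, is shown for the same categories. This stands.

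Two stronger readings are tempting. A reader might infer that all follow-up between visits is lost; it is not, since only time after the last visit is dropped. A reader might also infer that the arm with more discontinuers must be more overstated. That does not follow: discontinuers who attend the safety follow-up visit have no gap, and no document gives an arm difference in telephone-only follow-up.

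**Conclusion.** The rule is internally inconsistent and its error has one direction. For the limited group followed for AEs beyond the last visit, events can be counted over time that is not credited to event-free subjects. With 10% discontinuing, the overstatement from telephone-only follow-up is about 0.5% to 3% under plausible assumptions and about 10% if every discontinuer is telephone-only with no visit in the 12 weeks after the last dose. The rate ratio moves by about 1% to 5% for 5% against 10% discontinuing in the middle and extreme cases, and not at all if telephone-only follow-up is balanced.

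These sizes rest on the assumed telephone-only share, gap, open-label uptake and spread of last doses. They also take every discontinuer to be followed to 12 weeks after the last dose. Withdrawals of consent, and discontinuers who stay in visits to Week 20, would make the effect smaller.

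This is a minor point, worth correcting because the correction is cheap. It does not call any safety conclusion into question.

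**What to change.** Use one window for numerator and denominator. Replace the sentence on event-free subjects in SAP 2.1.4.2 with wording such as:

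*For subjects who do not experience the event, time at risk runs to the last date on which AE status was ascertained within the Table 2-1 period (visit or documented remote or telephone contact; the EOS date where the subject has ended the study, or the DB End of Treatment visit for OLE entrants), not later than the analysis cut-off. Events with onset after that subject-level date are not counted in the exposure-adjusted rate.*

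Add that a contact made only because a subject volunteers an event does not extend that subject's date; otherwise the mismatch returns.

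Simply running event-free time to the cut-off would be shorter, but it would credit completers awaiting Week 20 with weeks in which AEs were not actively sought, and so push rates down. Table 2-1 also does not define its period end as the last AE contact.

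The cost is minor programming and the use of contact dates. The EOS date is already on the Study disposition eCRF page; the documents do not show whether telephone-contact dates are in the database, so that needs checking. A few late volunteered events may leave the exposure-adjusted rate but stay in the crude incidence. Efficacy, alpha and patient management are unaffected.
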